#### **6.6.1 Maximum duration of dose hold**

Subjects are allowed to remain on study following a delay of up to 21 days due to SPH4336-related toxicity. Subjects who experience a delay of  $>$  21 days due to SPH4336-related toxicity may be permanently discontinued from further SPH4336 administration.

#### **6.6.2 Criteria for resumption of dosing**

If a dose hold is implemented for SPH4336-related toxicity, in addition to the criteria listed in [Table 3](#), subjects may restart study drugs only if the following conditions are met:

- No more than 21 days has passed since the last dose of SPH4336;
- The AE is not expected to recur (per the Investigator and Medical Monitor) at the same grade with resumption of SPH4336 based on an intervention such as the addition of a prophylactic treatment (e.g., prophylactic anti-emetics), or a reduction in the dose of SPH4336; and,
- Continued administration of SPH4336 is considered to be in the subject's best interest (per the Investigator).

#### **6.6.3 Dose re-escalation**

In subjects who undergo dose reduction, re-escalation may be considered if the following criteria are met:

- The toxicity responsible for the prior dose reduction is considered unlikely with return to the prior higher dose based on a change in subject status or treatment (e.g., successful medical management of underlying condition, uncertain relationship of prior toxicity to SPH4336); and,

- Approval of the Medical Monitor.

After dose reescalation, if the toxicity recurs and requires another dose reduction, the subject is not allowed to return to the higher dose level.

## **6.7 Overdose**

Any instance of overdose (suspected or confirmed and irrespective of whether or not it involved SPH4336) must be communicated to Shanghai Pharma Biotherapeutics USA Inc. or a specified designee. Details of any signs or symptoms and their management should be recorded including details of any antidote(s) administered.

## **6.8 Discontinuation**

SPH4336 may be discontinued in the event of any of the following:

- Clinically and or radiologically significant progressive disease;
- Unacceptable adverse event(s) considered secondary to SPH4336 despite appropriate therapy;
- Withdrawal of consent for SPH4336 administration by the subject (subject may agree to continue to be followed for safety and long-term outcome endpoints);
- Noncompliance by the subject as determined by the Investigator with agreement from the Medical Monitor and the Sponsor Medical Officer or designee; or,
- Termination of study by the Sponsor.

# **7 SAFETY**

Safety assessments will consist of monitoring and recording AEs and Serious AEs (SAEs), measurement of protocol-specified hematology, chemistry, urinalysis, vital signs, and other protocol-specified tests that are deemed critical to the safety evaluation of the SPH4336.

The Principal Investigator is responsible for recognizing and reporting AEs to the Sponsor or designee. It is the Sponsor's responsibility to ensure the reporting of relevant SAEs to the applicable local, national, or international regulatory bodies. In addition, Investigators must report SAEs and follow-up information to their responsible Institutional Review Board (IRB)/Ethics Committee (EC) according to the policies of that IRB/EC.

The Principal Investigator is also responsible for ensuring that every staff member involved in the study is familiar with the safety reporting requirements.

## **7.1 Adverse Events**

An AE is any untoward medical event that occurs to a subject following signing of the study Informed Consent Form (ICF), whether or not the event is considered SPH4336-related.

### Abnormal Laboratory Values

Not every laboratory abnormality qualifies as an adverse event. A laboratory test result must be reported as an adverse event if it meets any of the following criteria:

- Is accompanied by clinical symptoms;
- Results in a change in study treatment (e.g., dosage modification, treatment interruption, or treatment discontinuation);
- Results in a medical intervention (e.g., potassium supplementation for hypokalemia) or a change in concomitant therapy;
- Is clinically significant in the Investigator's judgment.

(Note: For oncology trials, certain abnormal values may not qualify as adverse events).

It is the Investigator's responsibility to review all laboratory findings. Medical and scientific judgment should be exercised in deciding whether an isolated laboratory abnormality should be classified as an adverse event.

If a clinically significant laboratory abnormality is a sign of a disease or syndrome (e.g., alkaline phosphatase and bilirubin 5xULN associated with cholestasis), only the diagnosis (i.e., cholestasis) should be recorded on the Adverse Event eCRF. If a clinically significant laboratory abnormality is not a sign of a disease or syndrome, the abnormality itself should be recorded on the Adverse Event eCRF, along with a descriptor indicating whether the test result is above or below the normal range (e.g., "elevated potassium," as opposed to "abnormal potassium"). If the laboratory abnormality can be characterized by a precise clinical term per standard definitions, the clinical term should be recorded as the adverse event. For example, an elevated serum potassium level of 7.0 mEq/L should be recorded as "hyperkalemia."

Observations of the same clinically significant laboratory abnormality from visit to visit should only be recorded once on the Adverse Event eCRF.

Pre-existing conditions are not considered an AE unless the condition worsens by at least one grade following the start of SPH4336 administration.

Adverse events will be captured starting at the time of informed consent. AEs occurring between the time of informed consent and the first dose of SPH4336 will only be captured if related to a study mandated procedure. AEs will continue to be captured until the sooner of 28 days after the last dose of SPH4336 or until a new anti-cancer treatment is started.

### 7.1.1 *Intensity and Causality of Adverse Events*

The event's **relationship to the study drug or treatment procedure** should be indicated according to the following definitions:

|                    |   |
|--------------------|---|
| Related     | The adverse event is related to the treatment or procedure. An adverse event (AE) is considered related if there is "a reasonable possibility" that the AE may have been caused by the study drug (i.e., there are facts, evidence, or arguments to suggest possible causation). |
| Not Related | The adverse event is clearly not related to the treatment or procedure.  |

The **frequency** of the event should be indicated according to the following definitions:

|                       |  |
|-----------------------|--|
| Single episode | This is the first and only experience/episode of the event in the trial. |
| Recurrent      | The event has occurred before in the trial.                              |
| Continuous     | The event is continuing.   |

The **intensity** grade of the event should be indicated according to the following definitions: All intensity of AEs will be assessed by the Investigator using NCI CTCAE v5.0.

The **outcome** should be indicated according to the following definitions:

|                                   |   |
|-----------------------------------|---|
| Recovered without sequelae | Patient recovered completely from the AE.   |
| Recovered with sequelae    | Patient has recovered from the AE but displays other symptoms.  |
| Ongoing                    | Patient continues to exhibit symptoms of the AE. The patient will be followed until the AE is resolved. |
| Death                      | Patient died (the date of death should be entered as the SAE resolution date).                          |
| Unknown                    | Outcome is unknown due to loss to follow-up.  |

### 7.1.2 *Time Period for AE Reporting*

AEs will be recorded as those that occur following signing the ICF through the sooner of 28 days after the last dose of SPH4336 or until the start of additional anticancer therapy. Treatment-emergent AEs will be recorded from the first administration of SPH4336 up to the sooner of 28 days after the last dose of SPH4336 or until the start of additional anticancer therapy.

### 7.1.3 *Reporting of Pregnancy*

Pregnancy is neither an AE nor an SAE. However, all pregnancies occurring in subjects, or their partner, will be followed to assess for pregnancy-associated AEs or SAEs such as congenital anomaly. If, at any time between the first study drug dispensing and 7 days after the last dose of study drug, a pregnancy is suspected, the patient/partner will be instructed/requested to return to

the study center within 48 hours and undergo a serum pregnancy test, as confirmation of pregnancy. All confirmed pregnancies must be immediately reported using the appropriate form.

Upon confirmation of a subject pregnancy, no further investigational treatment will be administered. All pregnancies with study drug exposure will be followed until resolution (i.e., termination [voluntary or spontaneous] or birth).

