**Table 1: Schedule of Assessments**

| Cycle                             | SCN      | C1 | C1 | C1  | C1 | C2 | C2 | C3+ | C3+ | ET  | SFU | LTFU |
|-----------------------------------|----------|----|----|-----|----|----|----|-----|-----|-----|-----|------|
| Day of cycle
( $\pm$ 2 days)   | -28 to 0 | 1  | 2  | 15  | 16 | 1  | 15 | 1   | 15  |     |     |      |
| Informed consent                  | X        |    |    |     |    |    |    |     |     |     |     |      |
| Medical history                   | X        |    |    |     |    |    |    |     |     |     |     |      |
| Weight                            | X        | X  |    | X   |    | X  | X  | X   | X   | X   | X   |      |
| Physical exam                     | X        |    |    |     |    |    |    |     |     |     |     |      |
| Symptom-directed exam             |          | X  |    | X   |    | X  | X  | X   | X   | X   | X   |      |
| Vital signs                       | X        | X  |    | X   |    | X  | X  | X   | X   | X   | X   |      |
| ECOG Performance status           | X        | X  |    |     |    | X  |    | X   |     | X   | X   |      |
| Adverse events                    | X        | X  |    | X   |    | X  | X  | X   | X   | X   | X   |      |
| Concomitant medications           | X        | X  |    | X   |    | X  | X  | X   | X   | X   | X   |      |
| 12-lead ECG                       | X        | X  |    | X   |    | X  | X  | X   |     |     |     |      |
| Hematology                        | X        | X  |    | X   |    | X  | X  | X   |     | X   | X   |      |
| Chemistry                         | X        | X  |    | X   |    | X  | X  | X   |     | X   | X   |      |
| Coagulation                       | X        | X  |    | X   |    | X  | X  | X   |     | X   | X   |      |
| COVID-19, HIV, TB, HBV, HCV tests | X        |    |    |     |    |    |    |     |     |     |     |      |
| Serum pregnancy test              | [X]      |    |    |     |    |    |    |     |     |     |     |      |
| Tumor assessment                  | X        |    |    |     |    |    | X  | [X] | [X] | [X] |     |      |
| Tumor tissue collection           | [X]      |    |    | [X] |    |    |    |     |     |     |     |      |
| PK samples                        |          | X  | X  | X   | X  | X  |    |     |     |     |     |      |
| SPH4336 compliance                |          | X  |    |     |    | X  |    | X   |     | X   |     |      |

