| Disease status                    |          |    |    |     |    |    |    |     |     |     |     | X    |

*Study assessments (biopsy, laboratory and clinic visits) may be performed  $\pm$  2 days of the recommended date. Laboratory assessments may be performed in advance of clinic visits.*

*Screening (SCN) is performed within 28 days of Cycle 1 Day 1 (C1D1). Screening evaluations may be repeated within 7 days of C1D1 if requested by the Medical Monitor (e.g., borderline eligibility or clinical instability)*

*End-of-Treatment (ET) visit is performed on day that decision is made to discontinue SPH4336 administration if the decision is made during a clinic visit. In subjects where the decision to discontinue SPH4336 administration is made outside of a clinic visit (e.g., based on scan results only available later), the ET visit may be combined with the SFU visit.*

*Safety Follow-Up (SFU) visit is performed 28 days ± 14 days after last dose of SPH4336.*

*ET and SFU visits may be combined if any of the following apply: 1) subject discontinued SPH4336 outside of a clinic visit, 2) subject had no Grade 2 or higher SPH4336-related toxicity at their last study visit or, 3) subject started a subsequent therapy.*

*Long-Term Follow-Up (LTFU) – Performed at 3-month intervals (±1 month) following last study visit (i.e., ET or SFU) on all subjects achieving at least stable disease and do not develop progressive disease while on treatment. LTFU of disease status will be performed until progression of disease, start of a new treatment, death or 12 months after last study visit, whichever is sooner. May be conducted via review of the medical record without the need for a clinic visit.*

*X - Required*

*[X] – Optional, or not performed on every visit (see notes below for specific assessments).*

*Informed consent – May be performed at any time prior to the start of screening procedures (i.e., outside of the 28-day screening window).*

*Medical history – Includes all cancer-related history over a subject's lifetime and non-cancer related history limited to the 2 years prior to C1D1.*

*Symptom-directed exam – Limited physical exam performed in response to symptoms reported by the subject.*

*Vital signs – Performed once on visit days. Vital signs to include heart rate (per minute), respiratory rate (per minute), blood pressure (mmHg), temperature (degrees Fahrenheit).*

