*Concomitant medications – Recorded from 28 days prior to C1D1 to the time of the ET or SFU visit, except for medications administered as cancer treatment, for which lifetime history will be recorded.*

*12-lead ECG – ECGs performed as close as possible to each PK draw. ECGs should be performed in triplicate (at least 5 minutes apart) if the QTcF on the initial ECG is greater than 470 msec. Additional ECGs may be collected if clinically indicated. On days without a PK draw, ECGs are performed once.*

*Hematology – [Blood] Complete blood count with differential to include WBC, RBC, HGB, HCT, platelets, MCV, MCH and differential*

*Chemistry – [Blood] Sodium, potassium, chloride, blood urea nitrogen, creatinine, glucose, calcium, AST, ALT, total, direct and indirect bilirubin, alkaline phosphatase, total protein, albumin*

*Coagulation – [Blood] PT, activated PTT (aPTT) and INR*

*Serum pregnancy test – [Blood] Only required for females of child-bearing potential*

*Tumor assessment – Performed at baseline and every 6 weeks (from C1D1) for 36 weeks, then every 12 weeks thereafter. Disease assessments may be performed less frequently if appropriate (e.g., subjects with complete responses) and approved by the Medical Monitor. Disease assessment should be performed using CT with contrast or MRI (if medically necessary).*

*PK sample(s) – [Blood] Collected in Cycle 1 Day 1: pre-dose and 1 h, 2 h, 4 h, 6 h post-dose, Day 2: 24 h post-dose and Day 15: pre-dose and 1 h, 2 h, 4 h, 6 h post-dose, Day 16: 24 h post-dose and in Cycle 2 (Day 1).*

*Tumor Tissue – Availability of archived tumor tissue or performance of a tumor biopsy during screening for confirmation of histologically of a liposarcoma with a dedifferentiated component and of CDK4 positivity, if not already known, in all subjects and for baseline tumor biomarker (phospho-Rb, Ki-67) determination in the first 10 subjects. A fresh biopsy will be collected on Cycle 1 Day 15 in the first 10 subjects to determine treatment-related changes in tumor biomarkers. Collection details are summarized in Section 5.4 and will be provided in the laboratory manual.*

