### 3 SUBJECT POPULATION

#### 3.1 Inclusion Criteria

- Informed consent
- $\geq 18$  years of age
- ECOG performance status 0 or 1
- Histologically confirmed, locally advanced or metastatic sarcoma
  - Dedifferentiated or well-differentiated/dedifferentiated liposarcomas
- No more than 3 prior lines of treatment
- Evidence of progression as evidenced by at least one of the following within the past 3 months:
  - An increase of at least 20% in measurable tumors
  - The appearance of new lesions
  - Unequivocal progression of non-measurable lesions
- Measurable disease per RECIST v1.1
- If residual treatment-related toxicity from prior therapy:
  - All treatment-related toxicity resolved to Grade 1 or baseline (alopecia excepted)
- ANC  $\geq 1,500/\mu\text{L}$
- Platelets  $\geq 100,000/\mu\text{L}$
- Hgb  $\geq 9.0 \text{ g/dL}$  (in the absence of pRBC transfusion over the prior 4 weeks)
- Estimated glomerular filtration rate of  $\geq 60 \text{ mL/min}$  (based on the Cockcroft and Gault formula for individualized estimates of GFR^3)
- Total bilirubin  $\leq 1.5 \times$  the Upper Limit of Normal (ULN) or  $\leq 3 \times$  ULN if known Gilbert's disease
- AST and ALT  $\leq 3 \times$  ULN or  $\leq 5 \times$  ULN if malignant involvement of the liver
- Sterile or willing to use effective contraception (approved hormonal contraceptive such as oral contraceptives, patches, implants, injections, rings or hormonally-impregnated intrauterine device (IUD), or an IUD in women of childbearing potential and a condom in men) during the study and for 3 months following the last dose of study drug
- Availability of archived tumor tissue or willingness to undergo a baseline tumor biopsy, and in the first 10 study subjects, to determine baseline tumor biomarker levels and a willingness to undergo a second tumor biopsy at C1D15 to assess treatment-induced changes in tumor biomarker levels

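### The recall-and-test instruction for a suspected pregnancy stops 7 days after last dose, although contraception is required for 3 months

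*Protocol*

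**What the plan says.** Protocol Section 7.1.3 sets a time-limited trigger. If, "at any time between the first study drug dispensing and 7 days after the last dose of study drug, a pregnancy is suspected", the subject or partner is to be brought back to "the study center within 48 hours and undergo a serum pregnancy test, as confirmation of pregnancy".

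The same section has two further duties with no such limit: "All confirmed pregnancies must be immediately reported using the appropriate form", and "All pregnancies with study drug exposure will be followed until resolution".

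The precaution period is set elsewhere. Section 3.1, and the synopsis in the same terms, requires effective contraception "during the study and for 3 months following the last dose of study drug".

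Protocol Table 1 has a row for "Serum pregnancy test" marked in the screening column only. Its note, "Only required for females of child-bearing potential", says who is tested and adds no time points. SAP Section 1.2 repeats this schedule. The Safety Follow-Up "visit is performed 28 days ± 14 days after last dose of SPH4336", and no pregnancy test is marked there, at End of Treatment or at Long-Term Follow-Up.

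**The concern.** By asking for 3 months of contraception, the sponsor treats that period as one in which a pregnancy should be avoided. Yet the protocol tells the site to confirm a suspected pregnancy only during the first 7 days of it. The protocol gives no reason for the shorter window.

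The immediate-reporting duty attaches to pregnancies that have been confirmed. After Day 7 nobody in the study is directed to confirm one, so confirmation, and the report that depends on it, relies on care outside the study. Partners are never scheduled for testing, so the Section 7.1.3 trigger is the only study-directed confirmation for them.

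What is at stake is prompt capture of exposed pregnancies for a drug that Section 1.7.1 describes as having limited human experience. The trial's efficacy inference is not involved.

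**Working it through.** The plan states no figure to reproduce. The check compares two post-dose windows and then reads the schedule for anything that bridges them.

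**Inputs**
- Recall-and-test window after last dose: 7 days (Protocol 7.1.3).
- Contraception period after last dose: 3 months (Protocol 3.1 and synopsis). Assumption: 90 days, with a range of 89 to 92 for calendar months.
- Safety Follow-Up: 28 ± 14 days after last dose (Protocol Table 1 notes).

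**Uncovered days** = contraception period − trigger window
- Central: 90 − 7 = 83 days; 83/90 = 92%.
- Range: 89 − 7 = 82 to 92 − 7 = 85 days; 82/89 and 85/92 are also 92%.

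**Does a scheduled visit bridge the gap?**
- Safety Follow-Up: 28 − 14 = Day 14 to 28 + 14 = Day 42. Unless it is combined with End of Treatment, the whole window falls after Day 7. No pregnancy test is listed at either visit.
- Long-Term Follow-Up: limited to subjects with at least stable disease who did not progress on treatment. It records disease status and may be done by chart review. Subjects who progress on treatment have no scheduled contact after Safety Follow-Up.

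**Share of the whole contraception period.** With T days of dosing, the uncovered share is 83/(T + 90). The values of T are illustrative and do not come from the protocol.

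| T (days of dosing) | Calculation | Uncovered share |
|---|---|---|
| 28 | 83/118 | 70% |
| 84 | 83/174 | 48% |
| 168 | 83/258 | 32% |

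**Conceptions late in dosing.** Suppose suspicion arises L days after conception (L is assumed). Conceptions in the last L − 7 days of dosing are then suspected only after the trigger has closed: 14 − 7 = 7 days if L = 14, and 28 − 7 = 21 days if L = 28. The short window can therefore miss pregnancies conceived on drug as well as those conceived afterwards.

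**The case against.** The strongest reply is that the two clauses do different jobs and need not match. One is an eligibility precaution. The other is an urgent recall rule, and one use of it, stopping the drug once a subject's pregnancy is confirmed, ends with dosing. The substantive safety duties already have no 7-day limit, a pregnancy confirmed elsewhere is equally reportable, and nothing bars a site from testing. Safety Follow-Up is also real clinical contact, with a symptom-directed exam and adverse event review.

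Much of this stands. There is no contradiction, and reporting and follow-up do not stop at Day 7. It is also true that a day count says nothing about consequence, and that the shares of the whole period depend on assumed dosing durations. Consent pages and the pregnancy form are not available for this review, so subjects or sites may have had instructions there. The point concerns the text of Section 7.1.3 only.

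What the reply does not answer is that immediate reporting depends on a confirmation the protocol stops directing after Day 7. On the assumed delays above, that is before pregnancies conceived late in dosing would be suspected. Clinical contact at Day 14 to 42 does not supply the missing instruction.

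The objection that few cases would arise is fair and limits the weight of the point. However, eligibility starts at 18 years with explicit childbearing-potential provisions, so the situation was foreseen.

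**Conclusion.** The concern holds, as a minor safety-procedure point. The confirmation trigger covers 7 of about 90 post-dose contraception days and leaves about 83 uncovered (82 to 85), with no scheduled test after screening to make up for it. The count rests only on converting 3 months to days. It measures calendar time, not risk or pregnancies missed.

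Practical weight is low: Protocol Table 2 gives a typical age of 50 to 60 for dedifferentiated disease, and SAP Section 5.7.2 records 14 patients enrolled before closure for futility. The primary endpoint, error rates and sample size are untouched.

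**What to change.** In Protocol Section 7.1.3, extend the end of the trigger from 7 days to 3 months after the last dose, so that it matches Section 3.1. On paper this takes the uncovered interval from 82–85 days to 0. No scheduled test is needed.

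The cost is one phrase, plus an occasional suspicion-triggered serum test and site contact after treatment. In a running trial it would be a protocol amendment needing IRB approval and an assessment of re-consent (Section 11.2). The longer window would also outlast adverse event capture, which under Section 7.1.2 ends at 28 days after last dose or at new anticancer therapy, if sooner. The change supplies an instruction but creates no new contact, so suspicion would still have to be raised by the subject, partner or site.

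Because this study has closed, the value lies with any subject still within 3 months of last dose and in not carrying the wording into later SPH4336 protocols.
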